3.4 Efficacy Evaluations

At the times indicated in Section 4 and the Table of Procedures and Assessments, scans will be obtained to evaluate response data for subjects enrolled in this study. Efficacy will be assessed according to criteria outlined in Section 6 (Efficacy Assessments) to evaluate the activity and potential benefit of the chosen treatments protocol in this subject population.

3.5 Biological Studies

Subjects will have an opportunity to participate in correlative biological studies on a voluntary basis. This study will be used to correlate *in vivo* and *in vitro* predictive drug responses. This study may be able to contribute to our knowledge of molecular determinants of response to therapy and/or development of biomarkers to help guide future therapy.

3.6 Treatment during waiting period

Subjects will be allowed to receive one cycle of standard of care or treating physician chosen therapy after their biopsy and before starting tumor board defined therapy in order to prevent progression during this waiting period. Subjects that opt to have this cycle of therapy will need to have recovered from hematological effects (to baseline) and have repeat scans of their primary tumor sites and any sites being followed for study efficacy before starting tumor board defined therapy.

4 SUBJECT SELECTION

4.1 Inclusion Criteria

1. Subjects must have proven pediatric cancer with confirmation at diagnosis or at the time of recurrence/progression and clinical determination of disease for which there is no known effective curative therapy or disease that is refractory to established proven therapies fitting into one of the following categories:
 - a. **Neuroblastoma**- Patients that have relapsed following standard of care therapy (such as high risk patients, patient presenting after age 15 months or MYCN amplified, and only following (for eligible patients) high-dose chemotherapy followed by hematopoietic stem cell transplantation and maintenance therapy with retinoic acid and antibody therapy) or having progressed during standard of care therapy and non-responsive/progressive to accepted curative chemotherapy.
 - b. **Brain Tumors**
 - i. **Medulloblastomas** (At relapse after standard of care therapy [surgery, chemotherapy and/or radiation] and/or non-responsive/progressive on accepted curative therapy)
 - ii. **Gliomas** (At relapse after standard of care therapy [surgery and/or radiation and/or chemotherapy] and/or non-responsive/progressive on accepted curative therapy)
 - iii. **Diffuse Intrinsic Pontine Glioma/DIPG/Diffuse Midline Tumor-** (At diagnosis, as there is no known curative therapy)
 - iv. **Glioblastoma Multiforme-** (At diagnosis, as there is no known curative therapy)
 - v. **Ependymomas** (At relapse after standard of care therapy [surgery with or without radiation] and/or non-responsive/progressive on accepted curative therapy)

- vi. Choroid plexus tumors (At relapse after standard of care therapy [surgery] and/or non-responsive/progressive on accepted curative therapy)
- vii. Craniopharyngiomas (At relapse after standard of care therapy [surgery or suppressive therapy] and/or non-responsive/progressive on accepted curative therapy)
- viii. Dysembryoplastic neuroepithelial tumors (DNETs) (At relapse after standard of care therapy [surgery] and/or non-responsive/progressive on accepted curative therapy)
- ix. Meningiomas (At relapse after standard of care therapy [surgery] and/or non-responsive/progressive on accepted curative therapy)
- x. Primitive Neuroectodermal Tumors (PNETs)/CNS Embryonal Tumors (At relapse after standard of care therapy [surgery, chemotherapy, and/or radiation] and/or non-responsive/progressive on accepted curative therapy)
- xi. Germ cell tumors (At relapse after standard of care therapy [surgery, and/or radiation and/or chemotherapy] and/or non-responsive/progressive on accepted curative therapy)
- xii. Atypical Teratoid Rhabdoid Tumor (ATRT) (At relapse after standard of care therapy [surgery, chemotherapy and/or radiation] and/or non-responsive/progressive on accepted curative therapy)

c. **Rare Tumors:**

- i. Soft tissue sarcoma
Rhabdomyosarcoma (At relapse after standard of care therapy [surgery, and/or radiation, chemotherapy] and/or non-responsive/progressive to accepted curative chemotherapy)
Non-rhabdomyosarcoma (At relapse after standard of care therapy [surgery, and/or radiation, chemotherapy] and/or non-responsive/progressive to accepted curative chemotherapy)
- ii. Bone
Ewings sarcoma (At relapse after standard of care therapy [surgery, and/or radiation, chemotherapy] and/or non- responsive/progressive to accepted curative chemotherapy)
Osteosarcoma (At relapse after standard of care therapy [surgery, chemotherapy] and/or non- responsive/progressive to accepted curative chemotherapy)
- iii. Renal
Wilms tumor (At relapse after standard of care therapy [surgery, and/or radiation, chemotherapy] and/or non- responsive/progressive to accepted chemotherapy)
Renal cell carcinoma (At relapse after standard of care therapy [surgery, chemotherapy] and/or non- responsive/progressive to accepted curative chemotherapy)
Malignant rhabdoid tumor (At diagnosis, as there is no known curative therapy)
Clear Cell Sarcoma (At relapse after standard of care therapy [radiation, chemotherapy] and/or non- responsive/progressive to accepted curative chemotherapy)
- iv. Germ Cell tumors (At relapse after standard of care therapy [surgery, chemotherapy] and/or non-responsive/progressive to accepted curative chemotherapy)

- v. Liver Tumors (At relapse after standard of care therapy [surgery, chemotherapy] and/or non- responsive/progressive to accepted curative chemotherapy)
- vi. Carcinomas- (At relapse after standard of care therapy and/or non- responsive/progressive to accepted curative chemotherapy)
- vii. Desmoid tumors- (At relapse after standard of care therapy and/or non- responsive/progressive to accepted curative chemotherapy)
- viii. Malignant Peripheral Nerve Sheath Tumors (MPNST)- (At diagnosis, as there is no known curative therapy)
- ix. Pheochromocytoma (At relapse after standard of care therapy and/or non- responsive/progressive to accepted curative chemotherapy).
- x. Ethesioneuroblastoma (At relapse after standard of care therapy and/or non- responsive/progressive to accepted curative chemotherapy).
- xi. Neuroendocrine tumors (At relapse after standard of care therapy and/or non- responsive/progressive to accepted curative chemotherapy).
- xii. Desmoplastic small round cell tumor (At relapse after standard of care therapy and/or non- responsive/progressive to accepted curative chemotherapy).
- xiii. Melanoma (At relapse after standard of care therapy and/or non- responsive/progressive to accepted curative chemotherapy).

2. Subjects must be age \geq 12 months at enrollment
3. Subjects must be age \leq 21 years at initial diagnosis
4. Subjects must have measurable disease as defined by RESIST v1.1 at the time of biopsy and tumor must be accessible for biopsy. Tumor samples submitted for analysis must contain $>50\%$ viable tumor tissue to qualify. In addition, subjects with disease confined to the bone marrow are eligible to enroll if the degree of marrow involvement is expected to be $>50\%$.
Note: Subjects who are expected to have no evidence of disease after surgical removal of their tumor are still eligible for this trial if their disease would normally require adjuvant chemotherapy treatment after surgery despite NED status.
5. Current disease state must be one for which there is currently no known effective therapy
6. Specimens will be obtained only in a non-significant risk manner and not solely for the purpose of investigational testing.
7. Lansky or Karnofsky Score must be ≥ 50
8. Subjects without bone marrow metastases must have an ANC $> 750/\mu\text{l}$ to begin treatment.
9. Subjects with CNS disease currently taking steroids must have been on a stable dose of steroids for 2 weeks prior to their biopsy and must not have progressive hydrocephalus at enrollment.
10. Adequate liver function must be demonstrated, defined as:
 - a. Total bilirubin $\leq 1.5 \times$ upper limit of normal (ULN) for age AND
 - b. ALT (SGPT) $< 10 \times$ upper limit of normal (ULN) for age
11. A negative serum pregnancy test is required for female participants of child bearing potential (≥ 13 years of age or after onset of menses)
12. Both male and female post-pubertal study subjects need to agree to use one of the more effective birth control methods during treatment and for six months after treatment is stopped. These methods include total abstinence (no sex), oral contraceptives ("the pill"), an intrauterine device (IUD), levonorgestrel implants (Norplant), or medroxyprogesterone acetate injections (Depo-provera shots). If one of these cannot be used, contraceptive foam with a condom is recommended.

13. Informed Consent: All subjects and/or legal guardians must sign informed written consent. Assent, when appropriate, will be obtained according to institutional guidelines

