2.3 Subject Enrollment and Sample Procurement and Data Processing

Eligible subjects will be enrolled onto this study at each site following a registration process that includes receipt of a signed subject consent form and a copy of the required baseline laboratory tests. Subjects will undergo a scheduled surgical resection and/or diagnostic biopsy procedure.

Common sample identifiers will be provided by the NMTRC Lead Study Coordinator to the participating site and will be used by all parties throughout the project to ensure sample, data and report alignment between participating organizations. At the time of tissue resection or biopsy, fresh tumor samples and a blood sample will be committed for this specific research study (referred to as “Primary Samples”), and prepared immediately per Appendix II and section 9.3. Primary Samples will be sent to Ashion Analytics, LLC, which is a CLIA-certified laboratory housed at the Translational Genomics Reserach Institute (TGen). Samples will be reviewed by local pathology to confirm that the sample sent to TGen contains >50% tumor cell viability which is the minimum required for successful analysis. The absence of an adequate tumor specimen from an enrolled subject will make them not eligible to continue on the study. Tumor

samples will also be sent for research purposes (referred to as “Secondary Samples.”) A portion of the tumor tissue biopsy will be shipped overnight to the [name] Pediatric Oncology Translational Research Laboratory on dry ice.

Upon arrival of the tumor specimens at Ashion and the [name] Pediatric Oncology Translational Research Laboratory, the samples will be logged and immediately processed according to details in Section 9.

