5.2 Screening

The Investigator is responsible for keeping a record of all subjects screened for entry into the study and subsequently excluded.

The following screening procedures must be performed within 21 days (14 days preferred) prior to date of biopsy*. Studies must be done *after* last previous treatment for malignancy:

1. Signed informed consent form. All subjects (or subjects' legal representatives) must provide written informed consent before any study specific assessments may be performed. Signed informed consent form for voluntary participation in correlative biologic analysis;
2. Complete medical and surgical history, including documentation of the evidence of malignancy and prior treatments for cancer. Include all other pertinent medical conditions and a careful history of all prior medical treatments;
3. Demographics;
4. Physical examination (including height and weight), noting all abnormalities and sites of palpable neoplastic disease;
5. Vital signs, including temperature, pulse rate, and blood pressure;
6. Karnofsky Performance status/Lansky Play status (Appendix I);
7. Complete Screening Baseline Symptom form;
8. CBC with differential;
9. Serum electrolytes (sodium, potassium, chloride, bicarbonate), blood urea nitrogen (BUN), creatinine, albumin, Bilirubin, ALT, and AST;
10. LDH and/or Specific Tumor Markers for defined disease (if available);
11. Serum pregnancy test for female subjects of child bearing potential (onset of menses or \geq 13 years of age);
12. CT or MRI of measurable disease sites (as indicated for tumor type);
13. Solid tumor biopsy for "Primary Sample" with remaining tumor tissue used in correlative biologic studies handled per section 9.3 and submitted per Appendix II.

For subjects that cannot provide a solid tumor biopsy; a bone marrow core biopsy sample will replace the solid tumor sample as the "Primary Sample." Bone Marrow must have adequate tumor (defined as >50% tumor) in order to qualify as "Primary Sample."

***NOTE: If standard-of-care sample collection occurred within 12 weeks prior to enrollment and after last previous treatment for malignancy, and frozen sample remains, a subject may enroll using previously collected samples. Samples must additionally have been snap frozen within 20 minutes of collection and kept in a -70/-80 freezer.**

14. Concomitant medications/therapies including documentation of steroid use and dose;
15. Confirmation of inclusion and exclusion requirements.

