Following completion of all required screening procedures and certification of all inclusion and exclusion criteria by the Investigator, the coordinator at the NMTRC will be contacted (via e-mail or phone call), at which time the subject will be enrolled in the trial and a unique subject number assigned.

The following screening procedures must be done prior to the first dose of study drug, but are not required to be done before biopsy.

1. MIBG/PET scan (if indicated for tumor type). Other imaging appropriate for tumor type may also be considered.
2. Any subject that is suspected to have possible bone marrow disease: Bone marrow aspirate and biopsy.
3. Completion (by study staff) of pre-study case report forms.
4. Any additional labs or testing required by the tumor board.

For subjects that receive one cycle of treatment while waiting to start tumor board defined treatment (per section 2.11) or if patient did not receive treatment but more than 28 days since last assessment has occurred prior to starting study treatment: The following additional screening procedures must be performed AFTER the last dose of this additional cycle of therapy and PRIOR to the first dose of tumor board defined treatment:

1. Repeat CT or MRI of primary disease sites and any disease sites being followed for study endpoints.
2. CBC with differential- subject must be hematologically recovered to baseline before starting tumor board defined treatment.

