7.3 Response Criteria

Overall response rate (ORR) in subjects with radiologically assessable disease will be determined by CT or MRI by cross-sectional imaging, MIBG/PET scans, and/or bone marrow assessment.

Response Assessment: Each subject will be classified according to their “best response” for the purposes of analysis of treatment effect. Best response is determined from the sequence of the objective statuses described below.

Response Criteria for Subjects with Solid Tumors: This study will use the (RECIST) Response Evaluation Criteria in Solid Tumor (version 1.1) from the NCI[44]. Key points are that a maximum of 5 target lesions are identified and that changes in the *largest* diameter (uni-dimensional measurement) of the tumor lesions are used in the RECIST v1.1 criteria.

- **Measurable disease:** The presence of at least one lesion that can be accurately measured in at least one dimension with the longest diameter at least 10 mm (CT scan slice thickness no greater than 5 mm). The investigator will identify up to 5 measurable lesions to be followed for response. Previously irradiated lesions must demonstrate clear evidence of progression to be considered measurable.
- Serial measurements of lesions are to be done with CT or MRI, using the same method of assessment is to be used to characterize each identified and reported lesion at baseline and during follow-up.

- Quantification of Disease Burden The sum of the longest diameter (LD) for all target lesions will be calculated and reported as the disease measurement.
- **Complete Response (CR):** Disappearance of all target and non-target lesions.
- **Very Good Partial Response (VGPR):** Greater than 90% decrease of the disease measurement for CT/MRI lesions, taking as reference the disease measurement done to confirm measurable disease at study entry. Non-target CT/MRI lesions stable to smaller in size.
- **Partial Response (PR):** At least a 30% decrease in the disease measurement, taking as reference the disease measurement done to confirm measurable disease at study enrollment. No new lesions or progression of any non-target measurable lesion.
- **Stable Disease (SD):** Neither sufficient decrease to qualify for PR or sufficient increase to qualify for PD from study entry.

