The assessment of response will include the initial measurable targets and will be performed after the second cycle, then after every other cycle (or 8 weeks, whichever occurs first). Serial results of bone marrow aspirates, biopsies and urinary catecholamines will be reviewed for responding subjects to confirm response or lack of progression.

Clinical Response

A subject will be defined as having a clinical response if they have stable disease or better and a decrease in their tumor markers by $\geq 50\%$. Clinical response will also be defined as a subject that has a complete clearing of a previously positive bone marrow while on study.

Progression Free Survival

Time to progression, defined as the period from the first day of administration of study drug until the criteria for progression are met taking as reference the screening measurements, will be assessed.

8 Sample Size Justification

Feasibility

Since this is primarily a feasibility trial, the definition of feasibility for this study will include:

“Enrollment onto study, genomic profile, analysis and report generation completed, tumor board held with treatment decision, treatment review completed, start of treatment, and completion of 1 cycle of therapy.”

Our preliminary results for 5 subjects indicates that we have a sample collection success rate of 5/5 (100%) subjects, a genetic report profile success rate of 5/5 (100%) within the 7-10 day time window as well as a treatment agreement success rate of 5/5 (100%) within the 5 day time window. The average time (+/-SD) for completion of the genetic profile was 6.6 days (+/-1.7 days) with a median of 7 days. The average time (+/-SD) for time to Treatment was 3.2 days (+/-0.8 days) with a median of 3 days. Data preliminary to date for each of these three feasibility markers are very consistent with our anticipated performance standards.

Our initial feasibility trial continues to show that it is feasible and safe to use RNA expression analysis and a DNA mutation panel for tumor boards creating treatment decisions for patients without curative options. This study will ask the feasibility of utilizing DNA exomes and RNA sequencing in a tumor for molecular guided therapy.

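### A tumor removed at the study resection can be scored as a CT/MRI response, because section 7.3 does not set evaluability and the reference measurement after surgery

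*Combined protocol and SAP*

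**What the plan says.** **Eligibility.** Protocol section 4.1, criterion 4, fixes measurable disease at the tissue procedure: "Subjects must have measurable disease as defined by RESIST v1.1 at the time of biopsy and tumor must be accessible for biopsy". Its Note adds that "Subjects who are expected to have no evidence of disease after surgical removal of their tumor are still eligible for this trial", provided the disease would ordinarily call for adjuvant chemotherapy. Section 2.3 allows the tissue procedure to be an operation: "Subjects will undergo a scheduled surgical resection and/or diagnostic biopsy procedure".

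**Imaging.** Section 5.2 states: "The following screening procedures must be performed within 21 days (14 days preferred) prior to date of biopsy". CT or MRI is on that list. A repeat CT/MRI before treatment is required after a waiting-period cycle, or when "more than 28 days since last assessment has occurred prior to starting study treatment". Surgery is not a trigger, and the repeat scan is not named as the new reference.

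**Response.** Section 7.3 describes the population this way: "Overall response rate (ORR) in subjects with radiologically assessable disease will be determined by CT or MRI". It does not say when the disease must be assessable. Partial response is measured against the enrollment measurement, very good partial response against the study-entry measurement, and assessment includes the initial targets. Complete response is "Disappearance of all target and non-target lesions". Clinical response needs "stable disease or better and a decrease in their tumor markers by" 50% or more, with no baseline value named. For MIBG/PET, by contrast, only subjects with a positive scan at the start of therapy are evaluable.

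**Analysis.** Section 12.4 reports response rates with exact 95% confidence intervals but gives no denominator and no rule for subjects without disease at treatment start. The synopsis counts anyone with a complete or partial response at any time on treatment as a responder, and compares ORR and PFS between the first and second 100 patients.

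**The concern.** ORR is meant to show the activity of the drugs that the tumor board selects. A lesion removed by the surgeon before the first dose says nothing about those drugs. If the reference measurement precedes the operation, the effect of surgery is credited to the treatment.

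The rate at stake is the first-listed measure of activity among the secondary objectives, and it is used to compare the two cohorts of 100. PFS has a milder form of the same problem: for a subject with no disease at treatment start it measures time to recurrence, whereas for the others it measures time to growth of existing disease.

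**Working it through.** The plan states no expected ORR and no ORR sample size, so there is no ORR figure to reproduce. Its only design figures are for feasibility in section 8. They reproduce: the probability of 5 or fewer successes in 9 is 0.746 at a rate of 50% and 0.166 at 75%. They do not bear on ORR.

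**Step 1: follow one subject through the rules.** Take a subject whose only tumor is wholly excised at the study resection.

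| Step | Rule (section) | Result |
|---|---|---|
| Entry | Measurable at biopsy; Note admits expected disease-free status (4.1) | Eligible, target lesions recorded |
| Baseline CT/MRI | Before biopsy or resection (5.2) | Shows the tumor |
| Reference | Enrollment measurement, initial targets (7.3) | Pre-operative sum |
| First assessment | After cycle 2 (7.3) | All targets absent |
| CT/MRI category | Disappearance of all lesions (7.3) | Complete response |
| Responder | Complete or partial response at any time (synopsis) | Yes |

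A post-operative scan with no disease cannot serve as the scan that confirmed measurable disease, so for this subject the written reference can only be the pre-operative one.

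**Step 2: partial resection.** If excised lesions make up a share r of the target sum and the rest is unchanged, the recorded decrease is r. With r of at least 30%, no new lesion and no progression of non-target disease, the subject meets the partial response rule.

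**Step 3: does the repeat scan close the gap?** The 28-day clock runs from the last assessment, not from surgery. A scan taken at the 21-day limit forces a repeat if dosing starts more than 28 − 21 = 7 days after the procedure. A scan taken on the day before forces one only after more than 28 − 1 = 27 days. In the earlier neuroblastoma feasibility trial (section 1.2), biopsy to treatment took 7 to 20 days. That trial used expression arrays, so its timing is only a guide. At 20 days, a scan done up to 28 − 20 = 8 days before surgery triggers no repeat. Some subjects will therefore have a post-operative scan before dosing and some will not, and neither case changes the written reference.

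**Step 4: size.** Let f be the share with no disease at treatment start and p the ORR among those with disease. If the first group is scored as complete responses:

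reported ORR = p(1 − f) + f, so the excess over p is f(1 − p).

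The documents give neither f nor p for this population. Assume p = 15%, and 5, 10 or 20 such subjects per 100:

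| Disease-free per 100 | Scored as complete response | Excluded | Excess |
|---|---|---|---|
| 5 | (0.15 × 95 + 5)/100 = 19.3% | 15% | 4.25 points |
| 10 | (0.15 × 90 + 10)/100 = 23.5% | 15% | 8.5 points |
| 20 | (0.15 × 80 + 20)/100 = 32.0% | 15% | 17 points |

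With 10 such subjects per 100 and p at the ends of the 10% to 35% range that section 1.2 quotes for relapsed neuroblastoma, reported ORR would be 0.10 × 0.90 + 0.10 = 19% and 0.35 × 0.90 + 0.10 = 41.5%, which is 9 and 6.5 points too high.

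**The case against.** The best defense is the limit to radiologically assessable disease. Read at treatment start, it removes a subject with nothing left to image. The MIBG/PET rule already works that way and suggests that this was the intent. The reading is reasonable, but it is not written for CT/MRI. At study entry, where criterion 4 requires measurable disease, the same words keep the subject in. So a reader might infer that these subjects are definitely counted in ORR. The documents support only that they are not clearly removed.

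A reader might also infer that such subjects could be scored as stable disease and sit in the denominator as certain non-responders. With the 15% assumption and 20 subjects, that would give 0.15 × 80/100 = 12%, and a spread of 32 − 12 = 20 points. The written rules do not lead there. Against the pre-operative reference, a fully excised tumor has shrunk by 100%, which rules out stable disease. Against a post-operative reference, the subject has no assessable disease and falls outside the ORR set. The comparison that stands is complete response against exclusion.

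On markers, section 5.3.1 repeats them, where available, at Cycle 1 Day 1 before study drug. A post-operative value therefore exists; what is missing is a statement that it is the baseline.

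Central handling helps only in part. Scans go to the coordinating center, but section 7.1 makes extramural review optional, and a central reader would still need a reference rule.

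Finally, ORR is secondary, and the Note is confined to disease that normally needs adjuvant chemotherapy, so the number may be small. Both points limit the consequence without supplying the missing rule.

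**Conclusion.** The point holds as a defect in the CT/MRI response rules. Section 7.3 sets no time at which disease must be assessable and ties response to a measurement that, for these subjects, precedes surgery. The written rules can thus score an excised tumor as a complete response and a partial resection as a partial response. They also leave room for a surgical fall in markers to count as clinical response. Because MIBG/PET evaluability is set at the start of therapy, the plan is inconsistent with itself.

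The size is illustrative: about 4, 8.5 or 17 points of excess ORR for 5, 10 or 20 disease-free subjects per 100, with an assumed true ORR of 15%. Nothing in the documents shows that the share differs between the two cohorts, so bias in that comparison is possible but not established. The primary feasibility endpoint and its two-stage test are untouched. This should be corrected before ORR is analyzed.

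**What to change.** In sections 7.3 and 12.4:

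- Define the ORR and clinical-response set as subjects with measurable or otherwise evaluable disease (imaging, MIBG/PET or marrow) remaining after the resection or biopsy and before the first dose.
- Remove wholly resected lesions from the target list, and use the latest post-operative scan before dosing as the reference where one exists.
- Name the Cycle 1 Day 1 value as the marker baseline.
- Classify subjects with no remaining disease as disease-free at treatment start and not evaluable for response. Assign this from the operative report and available imaging, without knowledge of later scans. Report their number and PFS on a separate line, by cohort.

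The cost is protocol and SAP wording plus one case report form field for disease status at Cycle 1 Day 1. Eligibility and treatment do not change, and no new scan is required. The downsides are a slightly smaller ORR denominator, and that partly resected subjects with no post-operative scan may not be evaluable on the resected lesion.
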